6.1 Adverse Events

Adverse events (AE) will be coded using the Medical Dictionary for Regulatory Activities (MedDRA) version 17.1.

A treatment-emergent adverse event (TEAE) is defined as an AE with start date/time on or after the start/time of fluciclovine (¹⁸F) administration, or AEs with worsening intensity on or after the start date/time of fluciclovine (¹⁸F) administration.

AEs with unknown start date/time will be assumed to be treatment-emergent unless the end date/time is known to be before the fluciclovine (¹⁸F) administration.

Summary tables will be produced for all TEAEs occurring up to 42 days (i.e. occurring between day 1 and day 43) after the fluciclovine (¹⁸F) administration.

An overall summary of TEAEs will be created including:

- number of TEAEs and number of subjects with TEAEs,
- number of TEAEs and number of subjects with TEAEs associated with the injection site,
- number of serious TEAEs and number of subjects with serious TEAEs,
- number of subjects with TEAEs by CTCAE grade (Grade 1 to Grade 5),
- number of subjects with TEAEs by relationship to fluciclovine (unrelated, possibly related, probably related, definitely related and related, where related adverse events are those classified as possibly, probably and definitely related to fluciclovine ¹⁸F)

The number and percentage of subjects experiencing TEAEs will be presented by system organ class (SOC) and preferred term (PT). System organ class and preferred term will be presented in decreasing frequency of the total number of subjects with TEAEs. If a subject experienced more than one treatment-emergent adverse event, the subject will be counted once for each system organ class and once for each preferred term.

The number and percentage of subjects experiencing TEAEs will be presented by SOC, PT and CTCAE grade. SOC and PT will be presented in decreasing frequency of the total number of subjects with TEAEs. If a subject experienced more than one TEAE, the subject will be counted once for each SOC and once for each PT at the worst severity.

The number and percentage of subjects experiencing TEAEs will be presented by SOC, PT and relationship to study drug. SOC and PT will be presented in decreasing frequency of the total number of subjects with TEAEs. If a subject experienced more than one TEAE, the subject will be counted once for each SOC and once for each PT at the closest relationship to study drug.

All adverse events will be listed and TEAEs will be identified. AEs occurring up to 42 days after fluciclovine (¹⁸F) administration will be flagged. All SAEs will be listed separately.

Date: 10OCT2018 Version: Amendment 1 Final

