7.7. Subsequent Visits

At each subsequent visit for the first 4 weeks following fluciclovine (^{18}F) PET/CT, study patients will be asked whether they have had any:

- Hospitalisations
- Consultations with other medical practitioners
- Disability or incapacity or other adverse event that has occurred since their last visit

24 (+ 4)-72 hours after fluciclovine (^{18}F) PET/CT (Telephone Visit 3)

A review of AE/SAEs will be performed via telephone consultation.

Outpatient appointment to review fluciclovine (^{18}F) PET/CT and revise management (Visit 4)

It is recommended that this outpatient appointment is scheduled approximately 2 weeks after the fluciclovine (^{18}F) PET/CT scan (Visit 2), although a window of 0-6 weeks is permitted depending on local clinical practice. The clinical team will then record whether the pre-scan management plan will be unchanged or altered based on the new information provided by the fluciclovine (^{18}F) PET/CT, and the reason for the decision. It is recognised that the revised management plan may be decided on before the outpatient appointment and this is permitted.

Examples of a change in proposed management plan include changing of treatment types and/or approaches (including change to radiotherapy plans), and recruitment into another clinical trial. The patient may enter another clinical trial as part of the management plan influenced by the PET/CT findings. Where an additional diagnostic procedure (e.g. imaging or biopsy) is performed in light of the PET/CT findings, the results of these should be considered prior to recording the revised management

plan, and this should be recorded on the CRF. The exception to this is where choline PET is performed in addition to fluciclovine (¹⁸F) PET/CT (see section 7.7).

The revised management plan will be discussed between the clinical team and participant, and the agreed management decision recorded. If the revised management plan and agreed management decision are different, the reason for the decision, including the influence of other standard of care assessments performed outside the trial protocol, will be documented.

The participant will also have an opportunity to report any AEs. A repeat set of clinical laboratory tests, urine dipstick analysis and ECG will also be performed during Visit 4 as part of a review for AEs.

1 month (+7 days) after fluciclovine (¹⁸F) PET/CT (Telephone Visit 5)

A review of AE/SAEs will be performed via telephone consultation.

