10.4. Procedures for Recording Adverse Events

All AEs observed by the investigator or reported by the patient up to 1 month after fluciclovine (¹⁸F) PET/CT are reported on the case report forms. A member of the research team will contact the participant by telephone 24 -72 hours and 1 month after completion of fluciclovine (¹⁸F) PET/CT to record any AEs that may have occurred after leaving the hospital. Patients will also attend a clinic visit 14 days post scan. All AEs reported by the patient will be clearly documented on the patient CRFs. The following information will be recorded: description, date of onset and end date, severity, investigator assessment of relatedness to fluciclovine (¹⁸F) injection, other suspect drug or device and action taken. Follow-up information should be provided as necessary.

AE severity

The National Cancer Institute's Common Terminology Criteria for Adverse Events (CTCAE) Version 4.03 (June 14, 2010) will be used to assess and grade event severity, including laboratory abnormalities judged to be clinically significant. The severity grading is provided below (Table 1).

Table 1. CTCAE (V4.03) AE Severity Grading

Severity (Toxicity Grade)	Description
Grade 1	Mild; asymptomatic or mild symptoms; clinical or diagnostic observations only; intervention not indicated.
Grade 2	Moderate; minimal, local or non-invasive intervention indicated; limiting age-appropriate instrumental ADL.*
Grade 3	Severe or medically significant but not immediately life-threatening; hospitalisation or prolongation of hospitalization indicated; disabling; limiting self care ADL**.
Grade 4	Life-threatening consequences; urgent intervention indicated.
Grade 5	Death related to AE

*Instrumental ADL refer to preparing meals, shopping for groceries or clothes, using the telephone, managing money, etc.

** Self care ADL refer to bathing, dressing and undressing, feeding self, using the toilet, taking medications, and not bedridden.

If the experience is not covered in the modified criteria, the guidelines shown in Table 2 below will be used to grade severity. It should be pointed out that the term “severe” is a measure of intensity and that a severe event is not necessarily serious.

Table 2. AE Severity Grading

Severity (Toxicity Grade)	Description
Mild (1)	Transient or mild discomfort; no limitation in activity; no medical intervention or therapy required. The subject may be aware of the sign or symptom but tolerates it reasonably well.

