11.2. Analysis of Outcome Measures/Endpoints

Evaluable patients are those that have had all baseline study measures recorded, including having had a fluciclovine (¹⁸F) PET/CT scan.

Evaluation of fluciclovine (¹⁸F) PET/CT

Evaluation of the fluciclovine (¹⁸F) PET/CT images will be primarily reviewed by site-based investigator(s) (as per standard of care). Image interpretation will be based on guidelines derived from an international fluciclovine (¹⁸F) reader consensus meeting held in June 2014. All readers will undergo training in interpretation of fluciclovine (¹⁸F) scans, and will have a training set available for reference. The investigators will have access to all the conventional imaging and medical record information.

The summary of findings will be documented on the appropriate CRF, in addition to a conventional imaging report issued as per standard of care in the respective institution.

Primary endpoint

The primary endpoint of clinical impact of fluciclovine (¹⁸F) in affecting treatment decisions will be assessed by record of the revised treatment plan post fluciclovine (¹⁸F) PET/CT scan in comparison to the pre-scan intended treatment plan.

Secondary endpoints

Improvement in outcome of radical salvage treatment based on fluciclovine (¹⁸F) PET/CT being included in the assessment.

This will be assessed as the proportion of these patients who have a treatment response or treatment failure, using the following definitions:

1. Treatment response
 - a. ≥50% decline in PSA [5] ±
 - b. Radiological response
2. Treatment failure
 - a. Increase or <50% decline in PSA ±
 - b. Radiological progression

PSA threshold

The positive detection rate will be calculated for the overall cohort and across a range of PSA values, to determine the optimum PSA threshold for lesion detection.

Safety assessment

Safety will be assessed from data on the occurrence of adverse events (AEs) and changes in clinical laboratory tests, vital signs, injection-site status, and physical examination findings from the time of administration of fluciclovine (¹⁸F) injection throughout the study period. This has been described in detail in Section 9.

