18. APPENDIX A: SCHEDULE OF STUDY PROCEDURES

Variables	Visit 1 (Screening, up to 14 days before Visit 2)	Visit 2 (Day of fluciclovine (¹⁸ F) injection and PET/CT)	Post-administration					Phone Visit 3 (24 -72 (± 4) hours after dose)	Visit 4 (Manag ement plan decision)	Phone Visit 5 (1 month ±7 days after dose)	Visit 6 (First day of management plan, may be same date as Visit 4)	Standard of care clinical follow-up (data entry at 6 months after starting management plan)	Patients who have radical salvage therapy		
			Dose	Immediately post scan	60 (±5) min	90 (±5) min	120 (±5) min						Pre-treatment PSA level (<31 days pre-therapy)	7-8 months after completing therapy	
Inclusion / exclusion criteria	X	X													
Informed consent	X														
Height, weight		X													
Medical history	X										X				
Measure PSA level	X											X		X	X
Record prior PSA levels	X										X			X	X
PCa treatment history	X														
Imaging history (3 months before to 6 months after PET/CT)	X										X			X	X
Intended management plan	X														
Concomitant medication and allergies	X	X													
Blood test	X								X						
ECG	X								X						
Post-screening pre- administration events		X													
Vital signs (heart rate and blood pressure)	X	X		X	X	X	X								
Urinalysis	X								X						
Injection site monitoring			X	X	X	X	X		X						
Imaging		X													
AE monitoring			X	X	X	X	X	X	X	X					
Revised management plan									X						
Agreed management plan									X						
Date of starting treatment											X				
Deviation from agreed management plan (if any)											X				
Treatment response assessment											X			X	X

19. APPENDIX B: Oxford site sub-study**Evaluation and optimisation of Bayesian penalised likelihood PET reconstruction for Fluciclovine (¹⁸F) whole body imaging***FALCON trial Oxford site sub-study*

[name], [name], [name] and Oxford FALCON trial investigators.

Background

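### SAP 6.1 tabulates TEAEs to 42 days, but scheduled adverse-event review reaches that far only for patients with a late Visit 4, so ascertainment after about 1 month is uneven

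*SAP*

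**What the plan says.** **Analysis window.** SAP 6.1: "Summary tables will be produced for all TEAEs occurring up to 42 days (i.e. occurring between day 1 and day 43) after the fluciclovine" administration. The AE listing uses the same limit, flagging "AEs occurring up to 42 days after fluciclovine" administration. Results are numbers of events and numbers and percentages of subjects. By SAP section 2 the default denominator is the analysis set, here the Safety Analysis Set. The SAP gives no reason for 42 days, and SAP 3.5 does not list it as a departure from the protocol.

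**Collection window.** The protocol gives several lengths:

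- Section 10.4, what goes on the case report form: "All AEs observed by the investigator or reported by the patient up to 1 month after fluciclovine" PET/CT.
- Section 7.7, when patients are asked: "At each subsequent visit for the first 4 weeks following fluciclovine" PET/CT.
- Section 7.7, Telephone Visit 5: "1 month (+7 days) after fluciclovine" PET/CT.
- Appendix A, the same call: "Phone Visit 5 (1 month ±7 days after dose".
- Section 7.7, Visit 4: about 2 weeks is recommended, but "a window of 0-6 weeks is permitted depending on local clinical practice". The visit includes an opportunity to report AEs, laboratory tests, urine dipstick and ECG. Section 10.4 describes a clinic visit at 14 days.
- Section 11.2, safety endpoint: from "injection throughout the study period".

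Appendix A marks no AE monitoring after Phone Visit 5. Under 7.7, Visit 6 (first day of the new management plan) may fall on the same date as Visit 4.

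**The concern.** A table headed as events up to 42 days will be read as a 42-day incidence after the tracer. That reading needs each patient to have been asked about the whole 42 days. Here the day on which asking stops depends on when Visit 4 and Visit 5 happen to fall, and Visit 4 timing is left to local practice. A patient last contacted on day 30 and a patient reviewed on day 42 each count as one full subject in the denominator.

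There is a second difficulty. If the new plan starts at a Visit 4 held at about 2 weeks, roughly 42 − 14 = 28 days of the window come after the start of androgen deprivation, salvage therapy or whatever else was chosen. SAP 6.1 has no rule that separates events by onset before or after that date.

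At stake is the interpretation of the overall, SOC/PT and CTCAE-grade TEAE tables. The primary endpoint is not affected.

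**Working it through.** **1. The SAP's own figure.** With the injection day counted as day 1, 42 days after injection is 1 + 42 = day 43. This agrees with SAP 6.1. Below, days are counted after the dose, so 23 days post-dose is SAP day 24.

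**2. Last scheduled AE contact.** For each patient this is the later of Visit 4 and Visit 5. The unreviewed tail is 42 − (later of Visit 4 day and Visit 5 day).

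**3. Visit 4 on time (about day 14).** Visit 5 is then the last contact. The documents do not give 1 month in days. I assume 30 and show 28 and 31. The tail is 42 − (month + tolerance); for example, Appendix A at its lower limit gives 42 − (30 − 7) = 19 days, and 19/42 = 45%.

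| 1 month taken as | Source | Visit 5, days post-dose | Tail to day 42, days | Share of 42 days |
|---|---|---|---|---|
| 30 | 7.7 (+7) | 30 to 37 | 12 to 5 | 29% to 12% |
| 30 | Appendix A (±7) | 23 to 37 | 19 to 5 | 45% to 12% |
| 28 | 7.7 (+7) | 28 to 35 | 14 to 7 | 33% to 17% |
| 28 | Appendix A (±7) | 21 to 35 | 21 to 7 | 50% to 17% |
| 31 | 7.7 (+7) | 31 to 38 | 11 to 4 | 26% to 10% |
| 31 | Appendix A (±7) | 24 to 38 | 18 to 4 | 43% to 10% |

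**4. Visit 4 at its upper limit.** 6 × 7 = 42 days, so the tail is 42 − 42 = 0. This patient is reviewed to the end of the SAP window, although 10.4 no longer requires AE recording at that point.

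**5. Direction of the effect.** Suppose 100 subjects, 20 of whom have a TEAE by the last call. If 0, 2 or 5 further subjects have a first TEAE recorded by day 42, the percentage is 20%, 22% or 25%. Lengthening the window cannot lower it. A person-time rate could fall: with no new events, 20/(100 × 23) = 0.87 per 100 patient-days becomes 20/(100 × 42) = 0.48. The SAP plans no such rate. The error is therefore a shortfall against true 42-day incidence, from events that occur in the tail and are never elicited.

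**The case against.** The best defence is that the SAP window fits the protocol. Visit 4 may take place up to 6 weeks after the scan, 6 weeks is exactly 42 days, and that visit carries an AE review. The window is just wide enough to hold every scheduled AE contact. The SAP does not say this, but it is a plausible origin. It explains the choice of cap without giving full coverage to patients seen at the recommended 2 weeks or so.

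The defence does rule out two stronger readings:

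- A reader might infer that no AEs are collected after 1 month. The documents do not support that. A late Visit 4 collects them, a Visit 5 held after day 30 is within both tolerances, and section 10.5 gives no end date for SAE reporting. Late ascertainment is uneven, not absent.
- A reader might infer that the longer window dilutes the AE rate. For counts and percentages of subjects it cannot, as step 5 shows.

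A reader might also want to cut the main tables at 1 month. That would drop findings from a permitted Visit 4 in weeks 5 to 6 and from a permitted Visit 5 after day 30. It would not remove treatment effects either, since the new plan can start well before 1 month.

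Other mitigation stands. TEAEs are also tabulated by relationship to fluciclovine, all AEs are listed, SAEs are listed separately, and cancer therapies are listed with start dates. The relationship table helps with attribution, but the overall, SOC/PT and grade tables remain mixed.

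**Conclusion.** The mismatch is real and minor. For a patient with an on-time Visit 4, and with 1 month taken as 30 days, the last 5 to 12 days (protocol 7.7) or 5 to 19 days (Appendix A) of the SAP window have no scheduled AE contact. For a patient seen at week 6 there is no gap. The tabulated percentages may therefore understate 42-day incidence, and the late part may include effects of newly started treatment.

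The shares of 12% to 45% measure the unreviewed part of the window, not the bias. They would equal the shortfall in event counts only under a constant event rate with no spontaneous reporting after the last call. The documents support neither assumption, and the tracer is a single injection with a half-life of about 110 minutes. The 45% figure also needs the lower limit in Appendix A, which 7.7 does not allow. The actual understatement cannot be computed from the documents.

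Separately, the endpoint period in section 11.2 is wider than what is collected. Follow-up continues for months after Visit 5 with no further scheduled AE monitoring.

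**What to change.** In SAP 6.1:

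- Keep the 42-day TEAE table, labelled as events recorded up to 42 days with incomplete ascertainment after Visit 5.
- Add a TEAE table from injection to each subject's Visit 5, the period about which every patient is asked.
- In both, separate or flag events starting on or after the first day of the new management plan.
- Report the day of last AE contact per subject, because Visit 5 itself varies.
- State why 42 days was chosen; if the reason is the Visit 4 window, say so.

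In the protocol, reconcile section 10.4 (1 month; clinic visit at 14 days), section 7.7 (4 weeks; +7 days; Visit 4 at 0 to 6 weeks) and Appendix A (±7 days). Restate the safety endpoint period as the actual AE collection window.

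The cost is small: one extra table, a date comparison using dates the protocol already has recorded (AE onset, visits, start of management), and a less sweeping statement of the safety period. SAP Addendum 2 documents analyses added after database lock, so the same route is available, with the additions marked as such.

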6.2 Clinical Laboratory Evaluation

6.2.1 Haematology

Haematology values will be summarised by parameter and visit, and also for change from baseline (last pre-scan value vs first post-scan value).

All haematology values will be listed showing reference ranges (flagging abnormal findings).

6.2.2 Biochemistry

Biochemistry values will be summarised by parameter and visit, and also for change from baseline (last pre-scan value vs first post-scan value).

Additionally, from the serum creatinine levels (mg/dL), creatinine clearance (CrCl) will be derived using the Cockcroft Gault formula (Cockroft DW, 1976) and the glomerular filtration rate (GFR) will be derived using the MDRD formula (Levey AS, 2006) as follows:

- Cockcroft-Gault formula: CrCl (mL/min) = [(140 age) * (Weight in kg) * (0.85 if female)] / (72 * Creatinine)
- MDRD formula: GFR (mL/min) = 175 * Creatinine^{-1.154} * age^{-0.203} * (1.212 if subject is black) * (0.742 if female)

CrCl and GFR categories (≤30 mL/min, >30 - ≤60, >60 - ≤90, >90 mL/min) will be summarised by time window, and the shift table of baseline status against the worst status on or after fluciclovine (¹8F) administration will be presented.

All biochemistry values will be listed showing reference ranges and flagging abnormal findings.

6.2.3 Urinalysis dipstick

All urinalysis results will be listed.

6.2.4 Urine microscopy

All urine microscopy results will be listed.

6.3 Vital Signs

Vital signs include pulse rate, systolic and diastolic blood pressure.

Vital sign values will be summarised by parameter and time point, and also for change from baseline.

Details of vital signs data will be listed.

6.4 Electrocardiography

Electrocardiogram (ECG) interpretation is recorded at screening and visit 4.

ECG interpretations will be summarised by shift tables highlighting any changes between screening and visit 4.

Date: 10OCT2018 Version: Amendment 1 Final

1 INTRODUCTION

This Statistical Analysis Plan (SAP) is based on the final protocol version dated 24th March 2015 and amendments 1-4 dated 30th November 2015, 5th April 2016, 2nd March 2017 and 4th June 2018.

The SAP describes the tables, listings and figures which will be provided upon completion of the study. The SAP will be finalised before locking the database.

The table, listing and figure shells will be supplied in a separate document.

2 GENERAL PRINCIPLES

The analysis and statistical reporting will be conducted at Syne qua non using SAS version 9.2 or higher.

All listings will be based on all enrolled subjects unless specified otherwise. All tables will be presented by site and overall for the appropriate analysis population.

Descriptive summary statistics for continuous variables will include number of subjects (n), mean, standard deviation (SD), minimum, median, and maximum, unless specified otherwise. The precision of these summary statistics is defined in the table, figure and listing shells document.

Descriptive summary statistics for categorical variables will include frequency counts and percentages [n (%)]. Unless stated otherwise, the denominator for percentage calculations will be the number of subjects in the analysis set.

For treatment response baseline prostate specific antigen (PSA) is the most recent PSA measurement prior to salvage therapy for subjects who had salvage treatment and the most recent PSA measurement prior to the 18F-fluciclovine positron emission tomography/computerised tomography (PET/CT) for non-salvage subjects. If no PSA measurement is available just prior to salvage therapy, baseline will be defined as the most recent PSA measurement prior to fluciclovine (¹⁸F) scan. For all other variables, and for baseline PSA other than for treatment response, baseline is defined as the most recent value prior to fluciclovine (¹⁸F) administration.

In general, there will be no imputation of missing data, however where dates are partially missing dates may be imputed for calculation purposes, details are given under relevant section.

